4.2. Secondary Objectives

The secondary objectives of the study are:

- To assess safety and toxicity profile of abemaciclib (i.e. to evaluate overall safety incidence and severity of TEAEs, SAEs, deaths, and clinical laboratory abnormalities)
- To evaluate the PK parameters of abemaciclib and its metabolites (i.e. to evaluate Steady-state concentrations of abemaciclib and its metabolites LSN2839567 and LSN3106726)

5. A Priori Statistical Methods

5.1. Sample Size Determination

The primary objective of this study is to evaluate the impact of 3 different meal settings on the incidence of severe diarrhea (\geq Grade 3) or prolonged Grade 2 diarrhea (>7 days duration) as well as dose reductions, dose interruptions, and treatment discontinuations due to diarrhea, and utilization of antidiarrheals for patients receiving abemaciclib monotherapy. This study will enroll up to approximately 100 patients to obtain approximately 20 patients who complete the primary outcome phase per meal administration condition. Randomization will be 1:1:1 to the 3 administration conditions and randomization will be stratified by region. The region is defined as: AMERIT (Russia, Ukraine, Turkey) vs Non-AMERIT (Belgium, Spain, Australia). The sample size is based on regulatory guidance, not statistical powering.

5.2. General Considerations

5.2.1. Populations

The following analysis sets will be defined for this study:

Intention-to-treat (ITT) analysis set: will include all randomized patients. The ITT analysis of efficacy data will consider allocation of patients to treatment groups as randomized and not by actual treatment received. This analysis set will be used for all baseline analyses and patient dispositions.

Per-protocol (PP) analysis set: will include all randomized patients who receive at least 1 dose of abemaciclib and do not have any major protocol violations that could potentially affect the conclusions of the study, such as significant noncompliance with meal administration conditions or abemaciclib treatment administration. This analysis set will be used for sensitivity analyses related to the primary objective.

For study Arm 1 (take abemaciclib with meal) and Arm 2 (take abemaciclib without meal), the PP analysis set will include all randomized patients who receive at least 1 dose of abemaciclib and who are at least 75% compliant with meal administration conditions and abemaciclib treatment administration.

For study Arm 3 (take abemaciclib without regard to food), the PP analysis set will include all randomized patients who receive at least 1 dose of abemaciclib and who are at least 75% compliant with abemaciclib administration.

Safety analysis set: will include all randomized patients who received any quantity of study treatment, regardless of their eligibility for the study. The safety evaluation will be performed based on the cohort assignment. The safety analysis set will be used for analyses related to the primary objective and for all dosing/exposure and safety analyses.

Pharmacokinetic analysis set: will include all enrolled patients who received at least 1 dose of abemaciclib and have at least 1 postbaseline evaluable PK sample and evaluable dosing information.

5.2.2. Definitions and Conventions

Study drug or **study treatment** refers to abemaciclib.

The **date of first dose** is the date of the first dose of study drug.

The **baseline value of a safety/efficacy assessment** is the last value observed prior to the first dose of study drug.

The **study day of a safety/efficacy event or assessment** will be calculated as:

- The difference between the date of the event or assessment and the date of first dose plus 1 for all events or assessments occurring on or after the day of first dose. For example, if an event occurs on 08JUN2014 and the date of first dose was 06JUN2014, the study day of the event is 3.
- The difference between the date of the event or assessment and the date of first dose for all events or assessments occurring before the day of first dose. For example, if an event occurs on 05JUN2014 and the date of first dose was 06JUN2014, the study day of the event is -1.

One month is defined as 365/12 days.

Unless otherwise noted, summaries of **continuous variables** will include a mean, median, standard deviation, minimum, and maximum.

Unless otherwise noted, summaries of **categorical variables** will include the frequency and percentage (relative to the population being analyzed) of each category.

5.2.3. Handling of Dropouts and Missing Data

General rules for imputing dates related to AE or concomitant therapy:

- Onset date of an AE or start date of a concomitant therapy:
 - If only the day is missing, the date will be set to:
 - First day of the month that the event occurred, if the onset yyyy-mm is after the yyyy-mm of first study treatment.
 - The day of the first study treatment, if the onset yyyy-mm is the same as yyyy-mm of the first study treatment.
 - If both the day and month are missing, the complete date will be set to:
 - January 1 of the year of onset, if the onset year is after the year of the first study treatment.
 - The date of the first dose, if the onset year is the same as the year of the first study treatment.
- Resolution date of an AE or end date of a concomitant therapy:

- If only the day is missing, the date will be set to the last day of the month of the occurrence, or to the date of death if the patient died in the same month.
- If both the day and month are missing, the date will be set to 31 December of the year of occurrence.

If a date is completely missing, then the AE will be considered treatment-emergent. In case of additional therapies, the therapy will be considered concomitant.

General rule for imputing other dates: If a date variable is needed for an analysis, use the following general rule to impute incomplete date:

- If the date has no missing year and month but the day is missing, then assign Day 1 to the day
- If the date has no missing year, but has missing month, then assign January to the month.

However, after imputation, check if the imputed date is logically consistent with other relevant date variable(s) and make appropriate correction if necessary. For example, if a visit start date was 10 May 2015 and a tumor assessment date was xx May 2015 (missing day) but it was known that it occurred after that visit, then after imputation, the tumor assessment date became 01 May 2015. In this case, the imputed tumor assessment date should be compared to the visit start date and then corrected to be the visit start date, 10 May 2015.

Safety analysis: The following rule for missing data processing will apply for safety analysis:

- Missing classifications concerning study medication relationship will be considered as related to study medication (both components).
- If the AE onset date is missing or partial, the date will be compared as far as possible with the date of first dose of study medication when determining whether or not the AE is present at baseline. In this case, the AE will be assumed to be treatment emergent, unless there is clear evidence (through comparison of partial dates) to suggest that the AE started prior to the first dose of study medication.

5.3. Patient Disposition

A detailed description of patient disposition will be provided, including a summary of the number and percentage of patients randomized, treated, as well as number and percentage of patients completing the study or discontinuing the study (by study arms/overall and by reason for discontinuation). A summary of all important protocol deviations will be provided.

5.4. Demographics and Baseline Characteristics

5.4.1. Demographics

Demographic characteristics will be summarized by study arms using descriptive statistics for randomized as well as for treated patients by race, ethnicity, age, age groups (<65 years, ≥65

years), height, weight, body mass index (BMI), country and region (AMERIT vs Non-AMERIT).

5.4.2. Disease Characteristics

Disease characteristics will be summarized by study arms using descriptive statistics for randomized as well as for treated patients. Disease characteristics will include the following: disease diagnosis, basis for diagnosis, and disease stage. In addition, the disease characteristics will include duration of disease (initial diagnosis to date of first dose), baseline Eastern Cooperative Oncology Group Performance Status (ECOG PS), HER2 status, Progesterone Receptor (PR) status and Estrogen Receptor (ER) status.

5.4.3. Historical Illnesses and Prior Therapies

Historical illnesses are events in the past that ended before the date informed consent is signed. Historical illnesses (coded according to the Medical Dictionary for Regulatory Activities [MedDRA]) will be listed for all treated patients.

Prior therapies, including systemic therapy, radiotherapy and surgeries will be listed for all randomized patients. Prior radiotherapy and systemic therapy will be summarized by the number of patients with at least one of each type of treatment, as well as by reason for regimen (e.g., palliative, curative, etc.). Additionally, the number of regimens of prior systemic therapy and (where available) the reason for prior regimens will be summarized.

5.4.4. Concomitant Therapy

Concomitant medications will be summarized by study arms and listed for the safety population.

5.5. Treatment Compliance

Treatment compliance information for study drug will be collected through capsule counts at each visit. The estimate of percent abemaciclib treatment compliance will be given by:

$$\text{Percent Treatment Compliance} = \frac{\text{actual cumulative dose taken}}{\text{expected cumulative dose to be taken}} \times 100$$

The actual cumulative dose taken will be determined based on counting the number of capsules returned at each visit and subtracting that number from the number of capsules dispensed over the course of the first 3 cycles. The expected cumulative dose to be taken will be determined based on the assigned dose and taking into account any dose reductions or omissions.

Compliance to the administration condition for Arm 1 and Arm 2 will be assessed as the proportion of doses during the first 3 cycles of treatment that are taken during the meal window allowed by the assigned administration condition.

The allowed meal window for Arm 1 (taken with a meal) would be taking abemaciclib during a meal or within 30 minutes of end of meal.

The allowed meal window for Arm 2 (taken without a meal) would be taking abemaciclib greater than 60 minutes before start of meal or taking abemaciclib greater than 120 minutes after end of meal.

There is no window for Arm 3 as the abemaciclib is taken without regard to food.

For each dose of abemaciclib taken during the first 3 cycles, the patient will record the administration condition in a diary. The compliance to the administration condition will be based on the available data obtained from diary.

Compliance with Morning Dose Diary, Evening Dose Diary and Bowel Movements Diary will be calculated as the proportion of the actual number of diaries and expected number of diaries.

In addition, timing of dose administration condition with respect to food intake timing may be summarized by study arms for morning and evening dose separately based on ed diary.

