Although food can change the bioavailability (BA) of a drug and may have clinically significant consequences, this has not been shown to be the case with abemaciclib. A food effect study has been conducted that evaluated the impact feeding status had on the exposure of abemaciclib. It was demonstrated that a high-fat, high-calorie meal (approximately 800 to 1000 calories with 150 calories from protein, 250 calories from carbohydrate and 500 to 600 calories from fat) administered to healthy subjects increased the area under the concentration versus time curve (AUC) of abemaciclib and its active metabolites by 9% and increased maximum concentration (C_{max}) by 26% (Verzenio® USPI). These changes in exposure were not clinically significant. Currently, abemaciclib is recommended to be taken with or without food (Verzenio® USPI).

In certain circumstances food may mitigate the local gastrointestinal (GI) toxicity of some drugs and this effect may be independent to any relationship between the feeding state and systemic absorption of the drug. To assess if the incidence and severity of the diarrhea associated with abemaciclib may be altered, this study in patients with previously treated HR+, HER2- mBC will evaluate the incidence of dose reductions, dose interruptions, and/or treatment discontinuations due to severe diarrhea (\geq Grade 3) or prolonged Grade 2 diarrhea (>7 days duration) when abemaciclib monotherapy is administered (200 mg orally [PO] BID) in the following feeding states; when abemaciclib is taken with a meal, when abemaciclib is taken in the modified fasted condition (defined as at least 1 hour before or 2 hours after a meal), or when abemaciclib is administered without regard to food in patients.

Overall Design:

Study I3Y-MC-JPCP (JPCP) is a multicenter, randomized, open-label Phase 2 study evaluating the impact of food on the incidence of severe diarrhea (\geq Grade 3) or prolonged Grade 2 diarrhea (>7 days duration) when receiving abemaciclib monotherapy 200 mg PO BID during the first 3 cycles of study treatment for patients with previously treated HR+, HER2- mBC.

Number of Patients:

The study will screen approximately 100 patients, of whom approximately 60 evaluable patients with HR+, HER2- mBC will be enrolled and randomized 1:1:1 to 1 of the 3 treatment arms as defined by different administration conditions. Randomization will be stratified by region.

Treatment Arms and Duration:

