7.1. Treatments Administered

Abemaciclib monotherapy will be administered 200 mg PO BID with specific administration conditions. Patients will be instructed to take their daily doses of abemaciclib either with a meal, without a meal in a modified fasting state (defined as at least 1 hour prior to or 2 hours after a meal), or without regard to food for the first 3 cycles. Patients will be requested to record the abemaciclib dosing and administration conditions followed in a diary. Abemaciclib will be taken on Days 1 to 28 of a 28-day cycle for each treatment arm. [Table JPCP.7.1](#) shows the treatment regimens.

Patients will be instructed to commence loperamide at the first sign of loose stools and thereafter as per local label. See [Section 7.7.1.1](#) for supportive management guidance. Patients will be required to record loperamide dose and frequency in a diary. Loperamide will be supplied or reimbursed by the sponsor according to local laws. If additional antidiarrheals are prescribed by the physician, they should be entered on the concomitant medication CRF.

Table JPCP.7.1. Treatment Administration

Study Arm	Drug	Dose, mg	Route of Administration	Dose Frequency	Administration Conditions
1	Abemaciclib	200	Oral	BID	Take with a meal
2	Abemaciclib	200	Oral	BID	Take without a meal; at least 1 hour before or 2 hours after a meal (modified fasted condition)
3	Abemaciclib	200	Oral	BID	Take without regard to food

Abbreviation: BID = twice a day.

The investigator or his/her designee is responsible for the following:

- explaining the correct use of the drug and planned duration of each individual's treatment to the patient/study-site personnel/legal representative.
- verifying that instructions are followed properly the first 3 cycles. Abemaciclib is taken as per the assigned study arm outlined in [Table JPCP.7.1](#).
- maintaining accurate records of abemaciclib dispensing and collection.
- returning all unused medication to Lilly, or its designee at the end of the study, unless the site is authorized by Lilly or its designee to destroy unused medication, as allowed by local law.
- educating the patient on the management of diarrhea as per [Section 7.7.1.1](#).

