9.1. Efficacy Assessments

Efficacy assessments are not applicable in this study. However, the investigator is required to confirm that the patient is still deriving benefit from study treatment and has no evidence of disease progression.

9.1.1. *Electronic Patient Diary Assessment*

Electronic patient diary (e-diary) assessment will collect number of bowel movements and diarrhea, thereby increasing the validity of measures reported by the patient and minimizing transcription errors in recording the measures. The use of e-diaries should also allow more frequent and timely interactions between investigator and patients. The system will be used to collect timing of abemaciclib doses taken relative to the time of their closest meal. Additionally, the e-diary system will incorporate reminders for patients to complete their diary.

Physicians and designated clinical staff will have access to the e-diary portal (secure web-based site) with the ongoing near real-time updating of patient reported diarrhea. Manual inspection of data will support patient safety monitoring, as well as the potential for reaching an optimum diarrhea management. Investigative staff can assess clinical data via the e-diary portal and recommend on dosing adjustments.

An instruction manual will be provided to patients and investigative sites. Additional instruction and training will be provided to the investigative sites regarding data collection, review, retention and archival processes. In the event of e-diary malfunction or loss, the patient will be instructed to immediately contact the investigative site for instructions regarding replacement of the equipment.

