10.3.1. Analyses Related to the Primary Objective

The primary analysis will evaluate each meal administration condition group for measures related to diarrhea in the first 3 cycles using the safety analysis set. Secondary analyses will be repeated using the per-protocol population.

- Incidence of severe diarrhea (\geq Grade 3)
- Incidence of prolonged Grade 2 diarrhea (defined as >7 days duration)
- Dose reductions due to diarrhea
- Dose interruptions due to diarrhea
- Treatment discontinuations due to diarrhea
- Utilization of antidiarrheals.

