5.8. Analysis Related to Primary Objective

The primary objective of the study includes the evaluation of the following endpoints over the first 3 cycles (primary outcome phase):

- Incidence of severe diarrhea (\geq Grade 3)
- Incidence of prolonged Grade 2 diarrhea (defined as >7 days duration)
- Dose reductions due to diarrhea
- Dose interruptions due to diarrhea
- Treatment discontinuations due to diarrhea
- Utilization of antidiarrheals

Analyses for each of these endpoints related to the primary objective will be summarized by treatment arm using safety analysis set population. For descriptive purpose, the odds ratios with 95% confidence intervals along with exact p-value using Fisher's Exact test will be produced for comparing arms with each other. In addition, incidence of severe diarrhea (\geq Grade 3) and incidence of prolonged Grade 2 diarrhea (defined as >7 days duration) will be combined into one endpoint. Dose reductions due to diarrhea, Dose interruptions due to diarrhea and Treatment discontinuations due to diarrhea will be combined into another combined endpoint. These two

combined endpoints will be summarized and analyzed using the same approach mentioned above.

The analyses for each of the endpoints related to the primary objective will be repeated using per-protocol analysis set population as a sensitivity analysis.

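### SAP 5.5 scores Arm 2 doses against a strict 60/120-minute limit, while the protocol gives patients an inclusive one, so a dose exactly on the instructed limit can be scored non-compliant

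*SAP*

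**What the plan says.** **Instruction to patients.** Table JPCP.7.1 in Protocol 7.1 gives the Arm 2 condition as "Take without a meal; at least 1 hour before or 2 hours after a meal (modified fasted condition"). The Synopsis and Protocol 3.1 repeat it: "defined as at least 1 hour before or 2 hours after a meal". The limits are inclusive.

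**Scoring rule.** SAP 5.5 sets the Arm 2 window as "taking abemaciclib greater than 60 minutes before start of meal or taking abemaciclib greater than 120 minutes after end of meal". The limits are strict. For Arm 1 the window "would be taking abemaciclib during a meal or within 30 minutes of end of meal", which includes its own limit. Arm 3 has no window.

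**Data behind the score.** SAP 5.5 bases the score on whatever diary data are available. Protocol 9.1.1 says of the e-diary: "The system will be used to collect timing of abemaciclib doses taken relative to the time of their closest meal". SAP 5.5 itself refers only to a meal and does not say which one.

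**Use of the score.** Protocol 10.3.3.3 and SAP 5.5 both define compliance with the administration condition as the proportion of doses in the first 3 cycles taken inside the window. SAP 5.2.1 then limits the per-protocol set in Arms 1 and 2 to patients "who are at least 75% compliant with meal administration conditions and abemaciclib treatment administration". Protocol 10.3.1 states: "Secondary analyses will be repeated using the per-protocol population". SAP 5.8 says that the primary-objective analyses "will be repeated using per-protocol analysis set population as a sensitivity analysis".

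**The concern.** The per-protocol repeat is meant to keep patients who followed their assigned meal condition. Under the SAP's strict limits, a patient who doses exactly 60 minutes before or exactly 120 minutes after a meal has done what the protocol asked, yet the dose can count as a failure. Round times such as one hour and two hours are the values a patient following the instruction might aim for or report.

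The discrepancy falls on one arm. Arm 1's limit is inclusive and Arm 3 has none, so only Arm 2 can lose instruction-following doses in this way. Food timing is the only planned difference between the arms, so a scoring rule that is stricter than the instruction in one arm makes both the compliance summary and the per-protocol comparison harder to interpret.

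**Working it through.** The plan states no figure for this point, so there is nothing to reproduce. The check compares the two texts and then counts doses.

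**Step 1. Score example doses.** The first two doses sit on an instructed limit. The closest-meal columns assume times stored to the minute.

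| Dose | Closest meal, strict (SAP) | Closest meal, inclusive (protocol) | Any meal may satisfy the rule, strict |
|---|---|---|---|
| 60 min before dinner, 240 min after lunch | fails (60 is not > 60) | passes (60 ≥ 60) | passes (240 > 120) |
| 120 min after breakfast, 180 min before lunch | fails (120 is not > 120) | passes (120 ≥ 120) | passes (180 > 60) |
| 30 min after breakfast, 240 min before lunch | fails (30 is not > 120) | fails (30 is not ≥ 120) | passes (240 > 60) |

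The inequality therefore decides the first two doses when scoring is against the closest meal. If any neighbouring meal may satisfy the rule, on-limit doses usually pass. The boundary problem depends on closest-meal scoring.

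**Step 2. Count the doses needed to lose per-protocol entry.**

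Inputs: twice-daily dosing on 28 days per cycle (Protocol 7.1), 3 cycles in the primary outcome phase, and the 75% threshold (SAP 5.2.1).

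- Planned doses: 2 × 28 × 3 = 168.
- Doses that must be in window: 0.75 × 168 = 126.
- Failures allowed: 168 − 126 = 42, so exclusion starts at 43.
- Check: (168 − 43)/168 = 125/168 = 74.4%, below 75%; 43/168 = 25.6%.
- If one of the two daily doses is habitually on the limit, 43 of 84 days (51.2%) is enough.

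**Step 3. Allow for other out-of-window doses.** These shares are assumptions, because the documents give none.

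| Other out-of-window doses | On-limit doses that exclude the patient |
|---|---|
| 0 | 43 (25.6%) |
| 17 (about 10%) | 43 − 17 = 26 (15.5%) |
| 34 (about 20%) | 43 − 34 = 9 (5.4%) |

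The first row only restates the 75% threshold. The other two show how little margin is left once some doses have already failed.

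**The case against.** The strongest objection is that the harm rests on facts the documents do not give. The mismatch matters only for doses recorded at exactly 60 or 120 minutes. Protocol 7.1 and 10.3.3.3 and SAP 5.5 speak of the patient recording the administration condition, which could be a category rather than clock times. Protocol 9.1.1 speaks of timing but gives no resolution. If categories are stored, the minute-level comparison may never be made. Nothing suggests that on-limit times are common. All of this stands. It limits the size of the point but does not remove the difference between the two texts.

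A reader might also infer that, because SAP 5.5 names no reference meal, the Arm 2 criterion is nearly empty: a dose 30 minutes after breakfast would pass on the strength of a distant lunch. The documents do not support going that far. SAP 5.5 scores the diary data, and Protocol 9.1.1 says the diary collects timing against the closest meal, so such a dose would be stored against breakfast. The protocol's own instruction is equally loose about which meal it means. Protocol 9.1.1 describes data collection and is not a scoring rule, so a one-line clarification is fair.

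Nor do the documents settle that closest-meal scoring is the right remedy. A dose 110 minutes after one meal and 90 minutes before the next passes on the closest meal (90 > 60) but fails if both meals must be cleared (110 is not > 120).

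**Conclusion.** The contradiction between SAP 5.5 and the protocol is real and can be read directly from the text. Its importance is minor. It touches two outputs: the meal-compliance summary and, through the 75% rule, membership of the per-protocol set used for the sensitivity analysis.

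A reader might infer that the primary result is at risk. It is not: the primary analysis uses the safety set, entry to which does not depend on meal compliance, and Protocol 10.3 plans no hypothesis tests. A reader might also take the dose counts as a forecast that patients will be excluded. They are thresholds only. They assume that all 168 planned doses are taken and recorded, times are stored to the minute, and scoring is against the closest meal. The share of on-limit doses is not in the documents, so no probability of exclusion can be stated, and the effect is negligible if such times are rare.

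**What to change.** Reconcile SAP 5.5 with Table JPCP.7.1 so that Arm 2 doses are scored with the same inequality patients are instructed to follow. If the e-diary stores categories rather than minutes, check that the category limits match that wording. Add one line to SAP 5.5 stating which meal or meals the score uses, consistent with what the e-diary collects.

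The cost is a few words in the SAP and one comparison operator in the program. The downside is that a few Arm 2 patients may move in or out of the per-protocol set. Making the limits inclusive can only add patients, whereas naming the reference meal or meals could remove some, depending on the reading a programmer would otherwise have chosen. The dosing instruction to patients need not change, and this point takes no view on which fasting window is clinically appropriate.
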